4.5.7 Electrocardiograms

A 12-lead ECG is required at screening and as clinically indicated. ECGs should be obtained on the same machine whenever possible. Lead placement should be as consistent as possible. ECG recordings should be performed after the patient has been resting in a supine position for at least 10 minutes.

For safety monitoring purposes, the investigator must review, sign, and date all ECG tracings. Paper or electronic copies of ECG tracings will be kept as part of the patient's permanent study file at the site. Any morphologic waveform changes or other ECG abnormalities must be documented on the eCRF.

4.5.8 Patient-Reported Outcomes

PRO data will be collected via questionnaires to more fully characterize the clinical profile of atezolizumab as a single agent and in combination with BCG. The questionnaires will be translated as required into the local language. To ensure instrument validity and that data standards meet health authority requirements, questionnaires scheduled for administration during a clinic visit should be completed prior to the performance of non-PRO assessments and the administration of study treatment. PROs are required at C1D1, and then every 6 weeks/2 cycles starting with C2D1.

The EORTC QLQ-C30 is a validated and reliable self-report measure (Aaronson et al. 1993; Hjermstad et al. 1995; Osoba et al. 1997) that consists of 30 questions assessing global HRQoL, five aspects of patient functioning (physical, emotional, role, cognitive, and social), three symptom scales (fatigue, nausea, and vomiting, and pain), and six single-items (dyspnea, insomnia, appetite loss, constipation, diarrhea, and financial difficulties) (see [Appendix 9](#)). Scale scores can be obtained for the multi-item scales. The EORTC QLQ-C30 takes approximately 5–10 minutes to complete.

The EORTC QLQ-NMIBC24 is a NMIBC-specific module that accompanies the EORTC. The validated and reliable self-report measure (Blazeby et al. 2014) consists of 24 questions assessing the following NMIBC-specific disease and treatment domains: urinary symptoms; malaise; future worries; bloating and flatulence; sexual function, enjoyment, intimacy, and problems; and intravesical treatment. Scale scores can be obtained for the multi-item scales (see [Appendix 10](#)).

4.5.9 Assessments during Treatment

All visits must occur within ± 3 days from the scheduled date unless otherwise noted (see [Appendix 1](#) and [Appendix 2](#)). All assessments involving cystoscopy and urine cytology will be performed within 21 days prior to atezolizumab treatment and for patients in Cohorts 1b, 2, and 3, 14–21 days prior to BCG dosing unless otherwise specified.

See the study flowchart provided in [Appendix 1](#) and [Appendix 2](#) for the schedule of treatment period assessments.

If scheduled dosing and study assessments are precluded because of a holiday, weekend, or other event, then dosing may be postponed to the soonest following date, with subsequent dosing continuing on the original 12-week schedule (for atezolizumab and BCG Induction course/Maintenance Course 1), 24-week schedule (for atezolizumab and BCG Maintenance Courses 2–5), or 21-day cycle schedule (for single-agent atezolizumab). If treatment was postponed for fewer than 3 days, the patient can resume the original schedule. Resumption of therapy beyond 3 days will require approval by the Medical Monitor.

Following the eighth cycle of atezolizumab, one of three subsequent administrations may be delayed by 28 days in the combination cohorts to allow for vacations. Following the eighth cycle of atezolizumab, one of three subsequent administrations may be delayed by 1 week for atezolizumab alone cohort to allow for vacations.

4.5.10 Treatment Discontinuation Visit

Patients who discontinue early from treatment for recurrence/progression or toxicity will be asked to return to the clinic within 30 days after the last administration of study treatment or before another anti-cancer therapy is initiated, whichever is earlier. The visit at which a tumor assessment shows progressive disease resulting in treatment discontinuation may be used as the treatment discontinuation visit.

See the study flowcharts provided in [Appendix 1](#) and [Appendix 2](#) for assessments to be performed at the treatment discontinuation visit.

4.5.11 Follow-Up Assessments

See the study flowchart provided in [Appendix 1](#) and [Appendix 2](#) for specified follow-up assessments.

Ongoing Tumor Assessments

Patients who discontinue study treatment for a reason other than disease recurrence/progression or cystectomy will continue to undergo tumor assessments per study protocol, until they experience disease recurrence/progression or cystectomy, until the patient dies, or withdraws consent, or until the study closes, whichever occurs first, for a maximum of 5 years after enrollment.

Patients who start a new anti-cancer therapy in the absence of disease recurrence/progression should continue to be followed for recurrence/progression according to the protocol schedule of response assessments unless consent is withdrawn or the patient experiences disease recurrence/progression or death or until study termination or withdrawal from study, whichever occurs first.

Adverse Events

See Sections [5.2–5.5](#) for information on reporting adverse events.

Survival and Subsequent Anti-Cancer Therapy Follow-Up

All patients will be followed for survival and subsequent anti-cancer therapy beginning 6 months after the treatment completion/discontinuation visit. Survival and subsequent anti-cancer therapy follow-up information will be collected via telephone calls, patient medical records, and/or clinic visits approximately every 6 months until loss to follow-up, death, withdrawal of consent, or study termination by the Sponsor, whichever occurs first, for a maximum of 5 years after enrollment. Request to withdraw from follow-up must be documented in the source documents and signed by the investigator. If the patient

withdraws from study treatment but not from follow-up, the study staff may use a public information source (e.g., county records) to obtain information about survival status only.

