There may be circumstances in which either BCG or atezolizumab is permanently discontinued, but it may still be possible to continue the remaining study treatment with approval of the Medical Monitor. Patients in Cohorts 1B, 2, or 3 (atezolizumab plus BCG) who discontinue atezolizumab after receiving fewer than three cycles may be replaced.

All patients will be closely monitored for serious adverse events or protocol-defined events of special interest for 90 days or 30 days for adverse events, following their last dose of study therapy (atezolizumab and/or BCG) or initiation of non-protocol anti-cancer therapy, whichever occurs first. Safety assessments will include the incidence, nature, and severity of adverse events, changes in selected vital signs and laboratory abnormalities graded per NCI CTCAE v4.0.

Serum and plasma samples will be collected to monitor atezolizumab pharmacokinetics and to detect the presence of antibodies to atezolizumab.

Patient samples, including archival tumor tissues, as well as plasma, whole blood, and urine will be collected for future exploratory biomarker assessments.

A treatment completion/discontinuation visit will be performed for all patients within 30 days after the last administration of study treatment.

[figure not shown]
Patients who discontinue study treatment for a reason other than disease recurrence/progression or cystectomy (e.g., because of toxicity) will continue to undergo tumor assessments per protocol until they experience disease recurrence/progression or cystectomy, until the patient dies, withdraws consent, or until the study closes, whichever occurs first, for a maximum of 5 years after enrollment.

In addition, all patients will be followed for survival and subsequent anti-cancer therapy beginning 6 months after the treatment completion/discontinuation until loss to follow-up, death, withdrawal of consent, or study termination by the Sponsor, whichever occurs first, for a maximum of 5 years after enrollment.

Figure 6 presents the treatment plans for each cohort. The schedules of assessments are provided in Appendix 1 and Appendix 2.

[figure not shown]
Figure 6 Treatment Plans

Cohort 1A

Cohort 1A: Patients receive atezolizumab 1200 mg IV q3w.

Cohort 1B

[figure not shown]

BCG = bacille Calmette-Guérin.

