- Patients with persistent and/or recurrent high-grade NMIBC (any pT1, high grade pTa, or CIS) on or after the 6-month biopsy will be discontinued from study treatment and offered the option to undergo cystectomy or other bladder-sparing modalities as is clinically appropriate. Patients who undergo cystectomy will be requested to submit additional tissue from their cystectomy specimens.
- Patients with evidence of disease progression to muscle-invasive or metastatic disease at any timepoint will be discontinued from study treatment.

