4.6.2 Study Treatment Discontinuation

Patients must discontinue study treatment if they experience any of the following:

- Persistence/recurrence of disease with high grade lesion (any pT1, high-grade Ta, or CIS) detected any time on or after the 6-month bladder biopsy.
 - Patients with persistent and/or recurrent high-grade NMIBC without progression at 12 weeks may continue in the study, provided there is no evidence of progression to muscle-invasive disease.
- Disease progression (e.g., muscle-invasive or metastatic UC)
- Symptomatic deterioration (i.e., uncontrollable pain secondary to disease or unmanageable ascites, etc.) attributed to disease progression as determined by the investigator after integrated assessment of radiographic data, biopsy results, and clinical status.
- Intolerable toxicity related to atezolizumab or the combination of BCG and atezolizumab, including development of an immune-mediated adverse event determined by the investigator to be unacceptable given the individual patient's potential response to therapy and severity of the event
- Any medical condition that may jeopardize the patient's safety if he or she continues on study treatment
- Use of another non-protocol anti-cancer therapy (see Section [4.4.2](#))
- Pregnancy

The primary reason for study treatment discontinuation must be documented in the eCRF.

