- ^x Primary assessment of tumor will be with cystoscopy and urine cytology. Tumor response assessment will occur every 12 weeks for the first 2 years, and every 24 weeks thereafter (or as clinically appropriate) until 5 years, and then yearly. White-light cystoscopy, narrow band imaging cystoscopy, or fluorescent (blue-light) cystoscopy will be acceptable for baseline assessment. The same methodology used to assess disease sites at screening should be used throughout the study except when medically contraindicated (e.g., the same cystoscopy protocol and urine examination). All known sites of disease must be documented at screening and re-assessed at each subsequent tumor evaluation. Random biopsies must include all four quadrants of the bladder. The same evaluator should perform assessments if possible to ensure internal consistency across visits. The Bladder Map template ([Appendix 11](#)) should be used to document the approximate size and location of any abnormalities, as well as the approximate location of any biopsies performed. For all patients, additional evaluation (imaging, exam under anesthesia, biopsies) should be performed at investigator discretion for any of the following circumstances:

Appendix 1

Schedule of Assessments: Cohort 1A (cont.)

- Abnormal cystoscopy
 - Positive urine cytology
 - Two sequential suspicious/indeterminate urine cytology specimens
- ^y Patients who discontinue all study treatment for a reason other than disease recurrence/progression or cystectomy will continue to undergo tumor assessments every 6 months until they experience disease recurrence/progression or cystectomy, until the patient dies, or withdraws consent, or until the study closes, whichever occurs first, for a maximum of 5 years after enrollment.
- ^z Health-related quality of life will be assessed using the EORTC QLQ-C30 and EORTC QLQ-NMIBC24.
- ^{aa} Concomitant medications include any prescription medications or over-the-counter medications. At screening, any medications the patient has used within the 7 days prior to informed consent should be documented. At subsequent visits, changes to current medications or medications used since the last documentation of medications will be recorded.

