Appendix 2 Schedule of Assessments: Cohorts 1b, 2, and 3 (cont.)

Study Procedures	Screening (Days –28 to –1)	Weeks 1–96 ^a	Disease Progression	Treatment Completion/ DC Visit ^b	Follow-Up
HIV, HBV, HCV serology ^q	x				
TB test ^r	x				
Serum pregnancy test ^{n, s}	x	q3w ^f		x	
Archival/screening FFPE tumor tissue specimen or 10 unstained slides ^t	x				
Serum PK sample ^u		See Appendix 5			
Serum ATA sample ^u		See Appendix 5			
Plasma PD Biomarker		See Appendix 5			
Atezolizumab infusion ^v		x			
BCG administration ^w		BCG Induction: weekly for 6 weeks (Weeks 0–11) BCG Maintenance Course 1: weekly for 3 weeks (Weeks 12–23) BCG Maintenance Course 2: weekly for 3 weeks (Weeks 24–47) BCG Maintenance Course 3: weekly for 3 weeks (Weeks 48–71) BCG Maintenance Course 4: weekly for 3 weeks (Weeks 72–95) BCG Maintenance Course 5: weekly for 3 weeks (Weeks 96–120)			
Tissue biopsy (mandatory sample) ^x		Prior to Cycle 9			

Appendix 2

Schedule of Assessments: Cohorts 1b, 2, and 3 (cont.)

Study Procedures	Screening (Days –28 to –1)	Weeks 1–96 ^a	Disease Progression	Treatment Completion/ DC Visit ^b	Follow-Up
Tissue biopsy (optional sample)			x	x	x
Tumor assessment ^y	x	Every 12 weeks following initiation of atezolizumab ^{y, l}		x ^z	x ^z
Patient-reported outcomes ^{aa}		Cycle 1, Day 1, Cycle 2 Day 1, and every 6 weeks thereafter		x	
Concomitant medications ^{bb}	x ^{bb}	x		x	
Adverse events ^{cc}	x ^{cc}	x		x	x
Survival and anti-cancer therapy follow-up assessment ^{dd}					x
Blood samples for pharmacodynamics and biomarkers ^{ee}		See Appendix 5			
Urine samples for biomarker analysis ^{ff}		See Appendix 5			
Whole blood TruCulture		See Appendix 5			
Whole blood FACS		See Appendix 5			

Appendix 2

Schedule of Assessments: Cohorts 1b, 2, and 3 (cont.)

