- ^y Primary assessment of tumor will be with cystoscopy and urine cytology. Tumor response assessment will occur every 12 weeks for the first 2 years, and every 24 weeks thereafter (or as clinically appropriate) until 5 years, and then yearly. Cystoscopy that falls prior to BCG should be performed at least 14 days prior to BCG administration. White-light cystoscopy, narrow band imaging cystoscopy, or fluorescent (blue-light) cystoscopy will be acceptable for baseline assessment. The same methodology used to assess disease sites at screening should be used throughout the study except when medically contraindicated (e.g., the same cystoscopy protocol and urine examination). All known sites of disease must be documented at screening and re-assessed at each subsequent tumor evaluation. Random biopsies must include all four quadrants of the bladder. The same evaluator should perform assessments if possible to ensure internal consistency across visits. Bladder Map template ([Appendix 11](#)) should be used to document the approximate size and location of any abnormalities, as well as the approximate location of any biopsies performed. For all patients, additional evaluation (imaging, exam under anesthesia, biopsies) should be obtained as clinical indicated or if progression is suspected, performed at investigator discretion for any of the following circumstances:
- Abnormal cystoscopy
 - Positive urine cytology
 - Two sequential suspicious/indeterminate urine cytology specimens
- ^z Patients with recurrent low-grade papillary disease will be required to undergo resection with TURBT (unless medically contraindicated) and may continue in the study and receive study treatment. Patients with persistent and/or recurrent high-grade NMIBC without progression at 12 weeks may continue in the study provided there is no evidence of progression to muscle invasive disease. Patients with persistent and/or recurrent high-grade NMIBC at the 6-month assessment will be discontinued from study therapy. Patients with progression to muscle invasion at any time will be discontinued from study therapy.
- ^{aa} Health-related quality of life will be assessed using the EORTC QLQ-C30 and EORTC QLQ-NMIBC24.

Appendix 2

Schedule of Assessments: Cohorts 1b, 2, and 3 (cont.)

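### Patients taken off treatment for high-grade NMIBC appear to leave tumor assessment without a PFS or bladder-intact DFS event, and 3.5.4 and 6.4.2 define these two endpoints differently

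*Combined protocol and SAP*

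**What the plan says.** **Stopping treatment.** Section 4.5.5 states the rule for residual disease: "persistent and/or recurrent high-grade NMIBC (any pT1, high grade pTa, or CIS) on or after the 6-month biopsy will be discontinued from study treatment"; 3.1.2 has the same rule. Section 4.6.2 lists "Persistence/recurrence of disease with high grade lesion (any pT1, high-grade Ta, or CIS) detected any time on or after the 6-month bladder biopsy" as one reason to stop and disease progression as a separate one.

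**Assessment after stopping.** Section 4.5.11 restricts it by reason for stopping: "Patients who discontinue study treatment for a reason other than disease recurrence/progression or cystectomy will continue to undergo tumor assessments per study protocol". Section 3.1.2 carries the same restriction and gives toxicity as its example: "Patients who discontinue study treatment for a reason other than disease recurrence/progression or cystectomy (e.g., because of toxicity) will continue to undergo tumor assessments". For Cohort 1A it is repeated in Appendix 1, footnote y: "Patients who discontinue all study treatment for a reason other than disease recurrence/progression or cystectomy will continue to undergo tumor assessments every 6 months". For Cohorts 1B, 2 and 3, the tumor assessment row of Appendix 2 reads "Every 12 weeks following initiation of atezolizumab" and is also marked in the Follow-Up column under footnote z. That footnote says "Patients with persistent and/or recurrent high-grade NMIBC at the 6-month assessment will be discontinued from study therapy" but does not say who stays under assessment. The general 12- and 24-week schedule in 3.1.2 and 4.5.5 has no limit by reason for stopping. All patients are contacted about every 6 months for survival and subsequent anti-cancer therapy (4.5.11).

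**Endpoints.** In 6.4.2, a PFS event is muscle-invasive progression, established by cystoscopy and urine cytology, or any death. A bladder-intact DFS event is muscle-invasive, regional or distant progression, bladder-cancer death or cystectomy, with other deaths censored. Section 3.5.4 puts no such limit on how PFS progression is established, and it counts every death in bladder-intact DFS. Patients without an event are censored when last known alive and event-free. Kaplan-Meier estimates are given by cohort, with 6, 12 and 18 months as example landmarks.

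**The concern.** Kaplan-Meier estimation assumes that censored patients have the same later risk as those who remain. Here a patient would be censored because high-grade disease was found, and section 1.1.4 itself links failure to reach CR after BCG induction with later progression and death. Progression after the exit would not be looked for on schedule, while deaths would still be collected. The 12- and 18-month estimates of PFS and bladder-intact DFS could then be biased, in a direction that depends on what is captured and on the censoring date.

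The two definition conflicts are a separate matter. As written, bladder-intact DFS is two different endpoints. It is also unclear whether muscle invasion first found on cystectomy histology counts for PFS.

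**Working it through.** **1. The plan's own figures.** For pooled Cohort 1 with N = 20, Table 11 gives 8/20 CR with (19%, 64%) and 9/20 with (23%, 68%). Clopper-Pearson limits reproduce both: 19.1-63.9% and 23.1-68.5%. These rates are illustrative. The plan gives no planning figure for PFS or bladder-intact DFS.

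**2. How many would leave near Week 24.** Patients without CR: 20 - 9 = 11 to 20 - 8 = 12. Patients with an earlier event must be removed. With an annual probability p converted to a hazard h = -ln(1 - p), and Week 24 = 0.46 years, the number leaving is 20 × (1 - CR) × exp(-(h_prog + h_death) × 0.46).

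Annual rates used:
- Progression in non-CR patients: 6% and 12%. Section 1.1.4 cites a 10-year PFS of 53.2% in BCG-refractory patients: 1 - 0.532^(1/10) = 6.1%. Section 3.4.1 cites 45% progression by 5 years in very-high-risk BCG-naive patients: 1 - 0.55^(1/5) = 11.3%. Neither is the population at issue.
- Progression in CR patients 5% and death 3%. These are assumptions with no source in the documents.

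Result: 10.2-10.5 of 20 at 45% CR and 11.2-11.5 at 40% CR. Non-CR on cytology alone lowers this slightly, because 4.5.5 does not accept cytology alone as progression. Two other groups raise the total over time. Responders with later high-grade recurrence must also stop: at an assumed 30-50% per year, about 13-15 of 20 have left by month 18. Stage or grade progression short of muscle invasion also ends treatment without an event.

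**3. Size and sign of the PFS bias.** Simulation of 1,000,000 patients with exponential times, 45% CR, the rates above and a cut-off at 120 weeks. Those leaving are non-CR patients who are event-free at Week 24. Under B, their later deaths count and the rest are censored at Week 24, the last tumor assessment. Under C, later deaths count and the rest are treated as progression-free to last contact.

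| Non-CR progression | True 18-month PFS | B (bias) | C (bias) |
|---|---|---|---|
| 6%/yr | 0.876 | 0.852 (-2.4) | 0.908 (+3.2) |
| 12%/yr | 0.832 | 0.840 (+0.8) | 0.893 (+6.2) |

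Closed-form check of the true values: 0.45 × exp(-0.0818 × 1.5) + 0.55 × exp(-0.0923 × 1.5) = 0.877, and with 0.1583 in place of 0.0923, 0.832. At 12 months the biases are -1.3 and +0.5 under B, and +1.7 and +3.3 under C. B can be negative because deaths are counted for patients whose event-free fellows have already been removed from the risk set.

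**4. Against sampling error.** The exact 95% interval for 17/20 is 62-97%. Estimates are by cohort, and before expansion Cohort 1A has up to about 12 patients and Cohort 1B 8-18.

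**5. The two bladder-intact DFS definitions.** If all assumed deaths are non-bladder-cancer, the 3.5.4 value equals the 6.4.2 value times exp(-0.0305 × 1.5) = 0.955. With an assumed 20-40% per year cystectomy rate in non-CR patients from Week 24, the 18-month values under 3.5.4 and 6.4.2 are 0.778 and 0.814 (6%/yr progression, 20% cystectomy), down to 0.653 and 0.683 (12%/yr, 40%). The definitions alone differ by 3-4 points.

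**The case against.** The strongest reply is that no section says assessment stops. The general schedule has no such limit, Appendix 2 marks Follow-Up assessment, and persistent disease is not literally recurrence or progression, which 4.6.2 lists separately. This stands as far as it goes: the exit is an inference. It is still the natural one. Sections 3.1.2 and 4.5.5 list persistent high-grade NMIBC under a heading on discontinuation for disease progression, and 4.5.11 follows patients on new therapy only while free of recurrence or progression. A rule that sites can read two ways needs settling in either case.

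A reader might infer that Appendix 2 sets the opposite rule. It does not. Footnote z repeats footnote l and may be a footnote error.

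It is also fair that capture is better than it first looks. Deaths are collected for everyone, and cystectomy dates are needed for cystectomy-free survival. The main gap is therefore muscle-invasive, regional or metastatic progression. The eCRF is not in the documents, so some of this may already be recorded.

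The PFS model is simple. It has no cystectomy, takes death as independent of progression, and would count deaths twice if the cited 10-year PFS already includes them. It shows that the sign is open and does not estimate the bias.

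**Conclusion.** The point holds as a minor one. On the natural reading, censoring of PFS and bladder-intact DFS depends on disease status from about month 6. About 10-12 of 20 pooled Cohort 1 patients would be affected near Week 24 at the Table 11 rates.

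Three stronger readings are not supported:
- That 11-12 of 20 is an upper bound. Later recurrences and lesser stage or grade progression add to it.
- That the estimates are known to be inflated. On the convention closest to 6.4.2 (B) the 18-month PFS bias is about -2 to +1 points. The +6 figure requires treating unassessed patients as progression-free to last contact, although a survival call does not establish that.
- That the trial's main results are at risk. Both endpoints are secondary and descriptive, the bias is below sampling error, and the 6-month CR rate, duration of CR and overall survival are unaffected.

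The bias figures rest on the assumed rates. The conflict between 3.5.4 and 6.4.2 rests on no assumption and is wrong as written. The rest is a cheap improvement.

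**What to change.** 1. At the existing 6-monthly survival and anti-cancer-therapy contacts (4.5.11; Appendix 1 footnote cc; Appendix 2 footnote dd), record for every patient from the medical record: the date of first muscle-invasive, regional or metastatic disease; the date and pathologic stage of any cystectomy; and the date last known free of these events. State in 6.4.2 that these dates set events and censoring for PFS and bladder-intact DFS.
2. Delete from the PFS definition in 6.4.2 the qualifier on cystoscopy and urine cytology, so that it matches 3.5.4. Leave the event set (muscle invasion or death) unchanged.
3. Reconcile 3.5.4 with 6.4.2 on non-bladder-cancer deaths in bladder-intact DFS. Reconcile 3.1.2, 4.5.5, 4.5.11, 4.6.2, Appendix 1 footnote y and Appendix 2 footnote z on who stays in tumor follow-up.

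Cost: a few eCRF fields, some of which may already exist, at contacts that already draw on medical records, plus wording. No added visit or procedure. The drawback is that dates taken from records are less regular than protocol assessments.
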